**b) Rapid inverse treatment planning on MVCT scans**

We have shown that accelerated treatment planning software for Helical TomoTherapy provides clinically acceptable dosimetry, with conformality and homogeneity that is superior to standard LINAC-based 3D conformal planning and is only slightly inferior to standard Helical TomoTherapy dosimetry (33). We have also shown that, with planning times of 2-5 minutes, this accelerated treatment planning software provides levels of dosimetric conformality, heterogeneity, and avoidance of organs at risk for simple SBRT treatments that are clinically equivalent to those generated with conventional Helical TomoTherapy treatment planning(39). This preliminary data supports that treatment planning speed is not likely to be rate limiting in the ultimate clinical implementation of the Scan-Plan-Treat STAT RT workflow.

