**b) Treatment Planning Speeds**

We will determine the speed of radiation treatment planning with our current clinical system and compare this to the speed of planning with newer in-development algorithms running on next generation computers with graphic processing units (GPUs). Since highly conformal radiation treatments must be routinely calculated in a few minutes for the Scan-Plan-Treat STAT RT workflow, we will determine if the treatment planning with GPUs is fast enough for clinical implementation (i.e. can be done in approximately 5 minutes). If not, we will optimize the planning process in collaboration with TomoTherapy, Inc to increase the speed of planning.

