### **7.3 Data Analyses Plans**

Treatment response as defined by International Bone Metastases Consensus Group will be determined for each patient. As described in Section 6.1.1, pain intensity as defined by the BPI and opiate use as quantified by the OMED will be used to categorize patients as having: Complete Response, Partial Response, Pain Progression, Stable Pain. At each evaluation, the patient's BPI and OMED at that visit will be compared to the pre-treatment levels. The "Worst Pain" score from the patient's BPI will be used to evaluate for treatment response. Patient response does not require a statistical analysis. The percentage of patients in each response category at each evaluation will be reported.

Patient pain will be recorded using the BPI before treatment and at designated evaluations after treatment. Pain scores before and after treatment will be compared using a Wilcoxon signed ranks test to determine if there is a statistically significant difference. Example: Pre-treatment vs. 1 week, Pre-treatment vs. 4 weeks, etc.

Analgesic use will be recorded by requiring each patient to keep a logbook of their analgesic intake. Their opiate intake for the last 72 hours will be converted to OMED at each evaluation and used in the categorization of treatment response. The difference between their OMED before and after treatment will be compared using paired two-sample t-tests.

Patients' functional status will be determined using the Karnofsky Performance Scale at each evaluation. The difference between the KPS before and after treatment will be compared using a Wilcoxon signed ranks test.

Patients' quality of life will be measured using FACT-BP and FACT-G scores at each evaluation. The difference between the FACT scores before and after treatment will be compared using a Wilcoxon signed ranks test.

Patient satisfaction will be measured using a modified version of FACT - TS – BTCSQ. No statistical analysis will be required for reporting the results. The average scores from the satisfaction survey will be reported.

To evaluate the CT detector dose calculations, the delivered radiation dose obtained using the phantom quality assurance will be compared to the exit radiation dose quality assurance calculation. The calculated dose and delivered dose for each patient will be compared using a paired two-sample t-test, and the % difference in dose will be reported.

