Contours generated from the conventional and experimental image registration flows will be compared in a variety of ways as described in Section 7.1. All comparisons of the contouring measures, including the Dice indices, will be performed using paired two-sample t-tests.

Toxicity will be recorded using CTCAE 4.0 criteria and RTOG Late Radiation Morbidity Scoring Criteria. The incidences of grade 3 or more toxicities will be reported.

The effectiveness of the infrared tracking system will be determined by comparing its position calculations with the position of the patient as determined by the position of the lasers with respect to the set up skin marks before and after treatment. The position changes calculated by each method will be compared using paired two-sample t-tests.

The average treatment planning speed of radiation treatment planning with our current clinical system will be calculated and compared the average speed of planning with newer in-development algorithms running on next generation computers with graphic processing units. These means will be compared with two-sample t-tests.

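### The planned comparison of mean planning speed does not answer the plan's own question: can GPU planning routinely be done in about 5 minutes?

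*Combined protocol and SAP*

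**What the plan says.** The combined protocol and SAP sets a decision question in section 7.1, item 2(b), Treatment Planning Speeds: "we will determine if the treatment planning with GPUs is fast enough for clinical implementation (i.e. can be done in approximately 5 minutes". The reason given there is that conformal plans must routinely be available within a few minutes. If the target is missed, the planning process is to be optimised further with the manufacturer. Section 1.3.9 allots the same step 3 to 5 minutes.

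Section 7.3 gives one analysis for this aim. It begins "The average treatment planning speed of radiation treatment planning with our current clinical system will be calculated and compared" with the average on the GPU algorithms, and ends "These means will be compared with two-sample t-tests".

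The other t-tests in section 7.3 are explicitly paired. For exit dose: "The calculated dose and delivered dose for each patient will be compared using a paired two-sample t-test". For contours: "All comparisons of the contouring measures, including the Dice indices, will be performed using paired two-sample t-tests". For infrared tracking: "The position changes calculated by each method will be compared using paired two-sample t-tests". The opioid-dose comparison is paired as well. Planning speed is the only t-test without that word. Neither section says which cases are timed on which system.

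**The concern.** The question that triggers action is about a threshold: is GPU planning fast enough, and reliably so? The planned analysis asks something else, namely whether the two averages differ. GPU planning could be clearly faster and still too slow, or no faster than an already quick clinical system and still fast enough. Section 7.3 specifies no comparison with 5 minutes, no interval on GPU time, no measure of spread and no share of plans finished in time. The decision in section 7.1 would therefore be taken without a pre-stated analysis behind it.

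A second, smaller matter is the design of the comparison. If the same study cases are planned on both systems, the data are paired and a paired analysis is the natural one. If different cases are used, the unpaired test is legitimate, but differences in case mix (target size, number of lesions) could account for part of any difference. The text does not say which applies.

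**Working it through.** **The plan's own figure.** The plan states no sample size, effect or SD for planning speed. Its only calculation is n = 21 for the pain-score comparison in section 7.2. That reproduces (signed-rank test, effect 2/3, two-sided 0.05, power 0.808) and is not in question.

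**Inputs.** From the documents: 30 patients and the 5-minute criterion. Assumed here: one timed plan per patient, and all planning times, SDs and correlations, since the documents give none of them.

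**1. Does the t-test track the criterion?** With 30 plans per system and common SD s:

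- t = (m1 − m2) / (s·sqrt(2/30)), on 58 degrees of freedom
- one-sided 95% upper bound on the GPU mean = m2 + 1.699·s/sqrt(30)
- share within 5 minutes, if times are normal = Φ((5 − m2)/s)

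| Clinical mean (min) | GPU mean (min) | SD | p, two-sample | Upper bound, GPU mean | Share within 5 min |
|---|---|---|---|---|---|
| 15 | 9 | 4 | 3e-7 | 10.24 | 16% |
| 10 | 8 | 2 | 0.0003 | 8.62 | 7% |
| 4.5 | 4.2 | 1.5 | 0.44 | 4.67 | 70% |
| 4.0 | 4.0 | 1.0 | 1.0 | 4.31 | 84% |

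The first two rows are significant and fail the criterion. The last two are not significant, yet the GPU mean is shown to lie under 5 minutes. They also show that a mean under 5 minutes can leave 16% to 30% of plans over it, so the mean and the share should be kept apart.

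**2. What would a direct analysis deliver with 30 plans?** For 30 of 30 within 5 minutes, the exact two-sided 95% lower bound is 0.025^(1/30) = 0.884. The corresponding bounds are 0.828 for 29, 0.779 for 28 and 0.735 for 27 of 30.

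**3. What does pairing change, if the same cases are used?** Let r be the within-case correlation and k the ratio of the two SDs. The variance of the paired difference is proportional to 1 + k² − 2rk; the unpaired analysis uses 1 + k². The ratio of standard errors is therefore sqrt(1 − 2rk/(1 + k²)).

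| SD ratio k | r = 0.3 | r = 0.5 | r = 0.7 |
|---|---|---|---|
| 1 (equal SDs, plausible on the log scale) | 0.84 | 0.71 | 0.55 |
| 1/10 (raw minutes, SD proportional to a 10-fold shorter mean) | 0.97 | 0.95 | 0.93 |
| 1/20 (raw minutes, 20-fold) | 0.98 | 0.97 | 0.96 |

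On raw minutes with a 10- to 20-fold speed-up, pairing reduces the standard error by only about 2% to 7%. The larger gains need similar SDs, which is plausible on log time.

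Ignoring a positive correlation is conservative. In simulation with 30 equal-variance pairs, the nominal 5% unpaired test rejected a true null in 2.0% of runs at r = 0.3, 0.7% at r = 0.5 and 0.1% at r = 0.7.

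**The case against.** The plan is not silent on GPU speed. Section 7.3 says the averages will be calculated, so the GPU mean can be set beside 5 minutes by eye. Section 7.1 also words the criterion loosely and fixes no pass mark for individual plans, so a proportion within exactly 5 minutes is one reasonable choice among several. Both points stand. They reduce the gap to a missing interval and a missing explicit comparison with the threshold, but they do not close it, because neither the t-test nor a bare average shows how often or how surely the target is met.

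The aim also carries little weight. Planning speed is not among objectives 2.2.1 to 2.2.3, and the secondary components stay outside direct patient care. Section 1.4 reports accelerated software "with planning times of 2-5 minutes" and does not expect this step to be rate limiting. All of that stands.

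A reader might infer that the t-test is simply the wrong test because the data are paired. The documents do not establish that. Pairing is a fair inference, since the word is missing for this t-test alone and a study case planned on GPU would also have its clinical plan. But the omission may be deliberate, and with different cases an unpaired test is sound. For the same reason, loss of precision (same cases) and case-mix bias (different cases) cannot both be charged against the plan.

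A reader might also take significance to be a foregone conclusion, given the 10- to 20-fold figure in section 1.3.9. That figure is stated as what GPU computing can achieve; it is not an assumption of this study.

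**Conclusion.** The point holds in a limited form. Section 7.1 sets a 5-minute criterion with a consequence attached, and the t-test of means in section 7.3 cannot decide it: a significant result can go with most GPU plans exceeding 5 minutes, and a null result can go with a GPU mean below 5 minutes. This rests on the text. The times in the illustrations are assumptions.

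The pairing question is subordinate and depends on which cases are timed, which the plan does not state. Any gain from pairing depends on a correlation and variances that the documents do not give. The reductions of 16% to 45% in standard error that a reader might compute from equal variances should not be quoted for raw minutes if the SD shrinks with a 10- to 20-fold shorter mean; there the gain is about 2% to 7%. Nor is there a false-positive problem, since ignoring positive correlation is conservative. The consequence is confined to an engineering decision, so this is a desirable improvement and not a serious defect.

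**What to change.** In section 7.3:

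1. Add an analysis of GPU planning time against 5 minutes: the proportion of plans completed within 5 minutes with an exact 95% interval, and/or a confidence bound on the mean GPU time. Say beforehand what result counts as fast enough, given that section 7.1 asks for routine performance. If a patient contributes more than one plan, say how those plans are handled, because the exact interval treats plans as independent.
2. State whether the same study cases are timed on both systems, preferably that they are. If so, replace the two-sample t-test with a paired comparison of log times and report the ratio of times with an interval. If not, keep the unpaired test and describe how the cases for each system are chosen.

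The cost is a few sentences in the plan. The one practical burden is re-planning study cases on the second system, if that is not already intended. No patient procedure or recruitment target changes.

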## **8.0 ADVERSE EVENTS AND REPORTING**

The treating physician is required to notify the UVA Data Safety Monitoring Board (DSMB), and the UVA Institutional Review Board (IRB-HSR) of any of any serious adverse event (SAE).

### **8.1 Definition**

#### **8.1.1 Adverse Event**

An adverse event is any undesirable medical experience occurring to a subject who has been given an investigational product, whether or not related to the study treatment(s). Medical conditions present before starting the investigational treatment/intervention will be considered adverse events only if they worsen after starting study treatment. The following are adverse events:

- All unfavorable, harmful or pathological changes in the general condition of a patient.
- Subjective or objective symptoms (spontaneously offered by the patient and/or observed by the Investigator or the study nurse).
- All intercurrent events or exacerbation of pre-existing diseases which occurred after the administration of the study treatment.
- All clinically significant changes in laboratory abnormalities.

- Any undesirable and unintended effect of research occurring in human subjects as a result of the collection of identifiable private information under the research.

AEs should be followed to resolution or stabilization, and reported as SAEs if they become serious (see below, definition of SAE). This also applies to patients experiencing AEs that cause interruption or discontinuation of investigational product, or those experiencing AEs that are present at the end of their participation in the study. Such patients should receive post-treatment follow-up as appropriate. AEs will be collected up to 30 days post last dose of study treatment in all cases including early study termination. If an ongoing AE changes in its severity or in its perceived relationship to study treatment, a new AE entry for the event should be completed.

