### **5.3 Final Study Visit**

The final study visit will occur at the 12 month visit. See the Time and Events Table for assessments that will be performed. Patients removed from study for treatment-related adverse events will be followed until resolution or stabilization of the adverse event

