### **8.1.3 Serious Adverse Event**

A serious adverse event or experience (SAE) or serious adverse drug reaction (ADR) is any adverse event temporally associated with the subject's participation in research that meets any of the following criteria:

- Death;
- Is life-threatening (places the subject at immediate risk of death from the event as it occurred);
- Requires inpatient hospitalization or prolongation of existing hospitalization;\*
- Results in congenital anomaly/birth defect;
- Results in a persistent or significant disability/incapacity;
- Important medical events that may not result in death, be life-threatening, or require hospitalization may be considered a serious adverse drug experience when, based upon appropriate medical judgment, they may jeopardize the patient or subject and may require medical or surgical intervention to prevent one of the outcomes listed in the definition. For reporting purposes, also consider the occurrences of pregnancy as an event which must be reported as an important medical event.

\*Hospitalization for anticipated or protocol specified procedures such as administration of chemotherapy, central line insertion, metastasis

interventional therapy, resection of primary tumor, or elective surgery, will not be considered serious adverse events.

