## **8.3 Serious or Unexpected Adverse Event Reporting Requirements**

This section may need revision if Sponsor or Funding Source of study has specific reporting requirements for trial, and/or if study is conducted under an IND.

For any serious or unexpected event which occurs to any patient in the course of their treatment on this study or within 30 days following cessation of treatment, the UVA Study Coordinator must inform:

- **The Principal Investigator verbally within 24 hours.**
- **Written report to the UVA Office of Clinical Research, DSMC, and IRB within 7 days.**

Collection of complete information concerning SAEs is extremely important. Thus, follow-up information which becomes available as the SAE evolves, as well as supporting documentation (e.g., hospital discharge summaries and autopsy reports), should be collected subsequently, if not available at the time of the initial report, and immediately sent using the same procedure as the initial SAE report.

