## **8.4 UVA Cancer Center DSMC AE Reporting Requirements**

All adverse events will be recorded on appropriate case report forms. In addition, AE Reporting will occur via the UVA Cancer Center clinical trials reporting system, C3TO (TABLE Below).

| Therapeutic Medium Risk Phase II Studies   |                         |              |              |          |                         |                      |                         |                      |           |
|---|-------------------------|--------------|--------------|----------|-------------------------|----------------------|-------------------------|----------------------|-----------|
| Reporting requirements for AEs that occur within 30 days of the last dose of protocol specified treatment |                         |              |              |          |                         |                      |                         |                      |           |
|   | Grade 1                 | Grade 2      |              | Grade 3  |                         |                      |                         | Grade 4 & 5          |           |
|   | Expected and unexpected | Expected     | Unexpected   | Expected | Without hospitalization | With hospitalization | Without hospitalization | With hospitalization | Expected  |
| Unrelated   | Not required            | Not required | Not required | C3TO     | C3TO                    | C3TO                 | C3TO                    | C3TO                 | C3TO      |
| Unlikely  |                         |              |              | 30 days  | 15 days                 | 30 days              | 15 days                 | 15 days              | 15 days   |
| Possible  | C3TO                    | C3TO         | C3TO         | C3TO     | C3TO                    | C3TO                 | C3TO                    | C3TO                 | C3TO      |
| Probable  | 30 days                 | 30 days      | 15 days      | 30 days  | 15 days                 | 15 days              | 15 days                 | 15 days              | (24-hrs)* |

|          |  |  |  |  |  |  |  |  |        |
|----------|--|--|--|--|--|--|--|--|--------|
| Definite |  |  |  |  |  |  |  |  | 7 days |
|----------|--|--|--|--|--|--|--|--|--------|

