## 8.5 UVA IRB Reporting Requirements

Reporting to the UVA HSR-IRB will follow the institutional plan as outlined in the table below. In addition, DSMC reports will be furnished to the IRB within 15 calendar days of study team's receipt of report.

| Type of Event  | To whom will it be reported: | Time Frame for Reporting   | How reported?   |
|--|------------------------------|--|---|
| Any internal event resulting in death that is deemed DEFINITELY related to (caused by) study participation (Note: An internal event is one that occurs in a subject enrolled in a UVa protocol.) | IRB-HSR                      | Within 24 hours  | IRB Online and phone call
www.irb.virginia.edu/   |
| Internal, Serious, Unexpected adverse event

Only for events as outlined in section 8.0.   | IRB-HSR                      | Within 7 calendar days from the time the study team received knowledge of the event.

Timeline includes submission of signed hardcopy of AE form. | IRB Online
www.irb.virginia.edu/  |
| Unanticipated Problems that are not adverse events or protocol violations  | IRB-HSR                      | Within 7 calendar days from the time the study team received knowledge of the event.   | Unanticipated Problem report form.
http://www.virginia.edu/vprgs/irb/HSR_docs/Forms/Reporting_Requirements-Unanticipated_Problems.doc |
| Protocol Violations (Note the IRB-HSR only requires that MAJOR violation be reported, unless otherwise required by your sponsor, if applicable.)

Or

Enrollment Exceptions          | IRB-HSR                      | Within 7 calendar days from the time the study team received knowledge of the event.   | Protocol Violation and Enrollment Exception Reporting Form

http://www.virginia.edu/vprgs/irb/hsr_forms.html   |

|             |  |  |  |
|-------------|--|--|--|
| Data Breach | The UVa Corporate Compliance and Privacy Office                | As soon as possible and no later than 24 hours from the time the incident is identified. | UVa Corporate Compliance and Privacy Office:
[contact]   |

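### Section 8.0 asks for notice of any SAE without time limit, but timed serious-event and DSMC reporting ends 30 days after treatment, so newly arising late serious events have no DSMC deadline

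*Combined protocol and SAP*

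**What the plan says.** All references are to the combined protocol and SAP.

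- **Open-ended duty.** Section 8.0 has the treating physician notify the DSMB and the IRB "of any of any serious adverse event (SAE"). It gives no end date and no deadline. Section 8.1.3 ties an SAE in time to the subject's "participation in research that meets any of the following criteria", and section 5.3 states "The final study visit will occur at the 12 month visit".
- **30-day limits.** Section 8.1.1: "AEs will be collected up to 30 days post last dose of study treatment in all cases including early study termination". In section 8.3 the study coordinator's reports (24 hours to the principal investigator, 7 days in writing to the Office of Clinical Research, DSMC and IRB) cover events "in the course of their treatment on this study or within 30 days following cessation of treatment". The DSMC table in section 8.4 is headed "Reporting requirements for AEs that occur within 30 days of the last dose of protocol specified treatment".
- **IRB table.** Section 8.5 has two relevant rows, neither with a stated window. The first is "Any internal event resulting in death that is deemed DEFINITELY related to (caused by) study participation", due within 24 hours. The second is internal, serious, unexpected events, due within 7 calendar days and qualified by "Only for events as outlined in section 8.0".
- **Late toxicity.** Section 1.5 defines it as occurring 3 months or more after treatment. It is part of primary objective 2.1.4, the section 5.1 table schedules toxicity evaluations to month 12, and section 7.3 reports Grade 3 or higher incidence.
- **Oversight.** Section 7.1 suspends the trial for safety review on counts of SAEs or of unexpected Grade 3+ toxicities, with no time window. Under section 9.2 the DSMC meets monthly and reviews how the stopping rules are applied.

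**The concern.** No passage says whether the open-ended duty in 8.0 or the 30-day limits govern. The duties also fall on different roles (treating physician in 8.0, study coordinator in 8.3) and name different bodies (DSMB in 8.0; DSMC in 8.3, 8.4 and 9.2).

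This matters more here than in a trial with only acute toxicity. The Grade 4 column of the RTOG late scale in Appendix F includes paralysis from cord injury, bowel and esophageal perforation, and spontaneous fracture. If such an event first appeared at month 6 and was judged related, one site could notify both bodies at once under 8.0. Another, following 8.1.1, 8.3 and 8.4, could leave it for routine review. At stake are the timeliness and consistency of safety oversight, partly while patients are still being enrolled. No efficacy estimate is affected.

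**Working it through.** The plan states no figure to reproduce. The check is a comparison of passages plus calendar arithmetic.

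**1. Rules side by side, for a new serious event at month 6**

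| Section | Recipient | Window | Deadline at month 6 |
|---|---|---|---|
| 8.0 | DSMB, IRB | none | notice due, no deadline |
| 8.1.1 | (AE collection) | last dose + 30 days | not collected as an AE |
| 8.3 | investigator, Office of Clinical Research, DSMC, IRB | treatment + 30 days | none |
| 8.4 | DSMC system | last dose + 30 days | none |
| 8.5, definitely related death | IRB | none stated | 24 hours |
| 8.5, serious unexpected | IRB | depends on what section 8.0 means | 7 calendar days, or possibly none |

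If the cross-reference in the last row means the opening sentence of 8.0, there is no window. If it means the whole chapter, the 30-day limits may come with it. On either reading the DSMC has no timed rule. A late serious event that is expected, and is not a definitely related death, has no IRB deadline either.

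**2. When the window closes**

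Inputs: last dose on day D, with D from 0 (limiting case) to 21 (section 4.6 completes treatment within 21 days); a 30-day window; 3 months taken as 91 days (assumption).

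- The window closes on day D + 30, so between day 30 and day 51 from treatment start.
- Late toxicity counted from treatment start: gap = 91 − (D + 30) = 61 − D, which runs from 61 days (D = 0) to 40 days (D = 21).
- Late toxicity counted from the last dose: gap = (D + 91) − (D + 30) = 61 days.

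The gap is positive in every case, so no newly arising late toxicity can fall inside the window.

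**3. Scheduled evaluations outside the window**

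- Section 5.1 toxicity row: the during-treatment column, week 1 and week 4 are inside. Weeks 8 and 12 and months 6 and 12 are outside, so 4 of 7. The tightest case is week 8 (day 56) against closure on day 51.
- The shorter list in the Study Overview (during treatment; weeks 4 and 12; months 6 and 12): 3 of 5 are outside.
- Week 12 is day 84, so only months 6 and 12 are clearly late toxicity.

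**4. Upper bound on late exposure while accrual is open**

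Inputs: 30 patients; accrual A = 18 months (sections 7.1 and 7.2) or 24 months (section 4.1); uniform accrual and no deaths (assumptions).

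- Planned late follow-up, months 3 to 12: 30 × 9 = 270 patient-months.
- Part falling before accrual closes: 30 × ∫₃¹² (A − u)/A du = 30 × (9 − 67.5/A), where 67.5 = (12² − 3²)/2.
- A = 18: 30 × 5.25 = 157.5 (58% of 270). A = 24: 30 × 6.1875 = 185.6 (69%).
- Patients reaching month 6 before accrual closes: 30 × (A − 6)/A = 20 or 22.5.

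These are ceilings. Entry requires only a life expectancy above 12 weeks (3.1.14), and section 5.4 expects losses to hospice. They measure exposure, not the number of reports that would be delayed; the documents give no late-event rate for this regimen as a whole.

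**The case against.** The best defence is that the protocol already has several nets.

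- **Section 8.0 covers any SAE, and the second row of 8.5 adds a 7-day IRB deadline.** Read literally, the only text directly under the 8.0 heading is the unlimited duty, so late serious unexpected events would have a timed IRB rule. This stands for the IRB on that reading. It gives the DSMC nothing and leaves expected events uncovered.
- **The DSMC meets monthly.** Section 9.2 lists all adverse events for review, 9.0 promises continuous monitoring by the investigator, and 8.4 has all adverse events recorded on case report forms without a window. If late toxicities enter that stream, the delay is about a month. This largely stands and limits the severity. But the stream is AE data, whose collection 8.1.1 ends at 30 days, and aggregate review is not expedited reporting.
- **An AE that becomes serious is reported as an SAE (8.1.1).** This holds for events that began earlier, not for newly arising ones.

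Three stronger readings are tempting, and the documents do not support them.

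- *Most late serious events have no reporting rule.* This cannot be counted. It depends on the 8.5 cross-reference and on which late effects are unexpected. Section 8.1.2 refers to product information for that, while section 4.10 lists seven expected toxicities, none of them a bone event.
- *Late toxicity is lost to the primary objective.* It is evaluated to month 12, and its Grade 3+ incidence is reported.
- *The stopping rule ignores late events.* Section 7.1 states no window and nothing ties it to 30 days, so its plain reading counts all events.

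**Conclusion.** The conflict is in the current text and should be fixed. Sections 8.1.1, 8.3 and 8.4 as written leave every newly arising late serious event without a timed DSMC report, in a trial where late toxicity is part of a primary objective and a stopping rule counts SAEs. IRB deadlines exist for definitely related deaths and, subject to the ambiguous cross-reference, for serious unexpected events. The defect is one of prompt and consistent reporting; capture of late toxicity and the efficacy analyses are untouched.

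The conclusion rests on the text and on the 40- to 61-day gap, which needs only 3 months taken as 91 days and the 21-day treatment limit. It does not rest on any assumed event rate. The exposure figures (at most 157.5 to 185.6 of 270 patient-months) show only that much late follow-up could coincide with open accrual.

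**What to change.** Reconcile sections 8.0, 8.1.1, 8.3, 8.4 and 8.5:

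1. Keep the notice of any SAE in 8.0. Without this, an extension limited to related events could narrow a duty that now covers unrelated SAEs too.
2. State that collection, and timed DSMC and IRB reporting, of SAEs and Grade 3+ toxicities at least possibly related to treatment run through the 12-month visit or death. Keep the 30-day window for other AEs.
3. Name one deadline, one responsible role and one recipient body, resolving DSMB against DSMC.
4. Say in 8.5 whether the reference to section 8.0 means its opening sentence or the whole chapter.
5. As a clarification, add to the stopping rules in 7.1 that qualifying events from all scheduled toxicity evaluations count, with thresholds and attribution categories unchanged.

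The cost is protocol wording and a few more expedited reports. No visit is added, because toxicity evaluations to month 12 are already scheduled. Section 8.5 follows an institutional plan and the 8.4 table is labelled for a class of studies, so study-specific wording beside those tables may be easier than editing them.
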